among young people. Preliminary evaluation data collected among an initial cohort of roughly 27,000 users has shown high levels of engagement in the program and high rates of abstinence among responders. Roughly ¾ of users set a quit date, with the most common quit date being the day of enrollment. Interactive keywords were used by 45.5% of teens and 38.4% of YA. Response rates to follow-up assessment questions were 36.9% at 14 days and 21.0% at 90 days. At 14 days, 60.8% of respondents indicated they had reduced or stopped using e-cigarettes altogether. At 90 days, 7-day point prevalence abstinence (ppa) was 25% and 30-day ppa was 16%. The high volume of enrollment in a short period of time, high levels of engagement with the program, and e-cigarette reduction and cessation results demonstrate that young people are interested in quitting vaping and can be engaged in an easily accessible, anonymous digital platform.

We recently completed an evaluation of This is Quitting with 2,588 young adults aged 18-24. Under an intention-to-treat analysis with missingness coded as vaping, abstinence rates were 24.1% among participants assigned to the intervention (This is Quitting) and 18.6% among participants in the assessment only control arm, a statistically significant difference (Odds Ratio=1.39, 95% CI 1.15-1.68, p< 0.001). [10]

Building on previous research, the primary aim of the current study is to conduct a comparative effectiveness trial to evaluate the effectiveness of *This is Quitting* in promoting abstinence from e-cigarettes among adolescents aged 13-17. This study is a 2-arm randomized controlled trial conducted among young users aged 13-17 recruited through online channels. Participants will be randomized to *This is Quitting* or an assessment-only control condition and followed for 7 months to roughly correspond to 6-months post-treatment. The secondary aim is to examine potential mediators of program effectiveness, including treatment engagement and changes in self-efficacy and perceived social support for quitting.

We will also include a waitlist control arm to evaluate the influence of assessment reactivity and retention incentives given relatively high quit rates among assessment-only control participants in the previous YA trial and the dearth of data on adolescent vaping cessation. This arm was not included in sample size calculations.

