The scientific, clinical, and public health communities are desperate for proven, evidence-based cessation resources to address the vaping epidemic among young people. We are uniquely positioned to address this urgent need given our extensive experience in conducting large-scale, rigorous research trials of digital tobacco cessation interventions and our expertise in working with young people. We plan to rapidly disseminate study results to benefit other researchers/service providers and use these results to further enhance the program.

METHODS

Subjects

We will randomize 1800 e-cigarette users aged 13-17 years old who are interested in quitting in the next 30 days to the two main intervention arms (900/arm). We will aim to randomize 450 to the waitlist control arm. Other eligibility criteria include past 30-day e-cigarette use and US residence. To fully enroll in the study, individuals must text a study-specific phone number and respond to the system-generated message.

Recruitment and Enrollment

Potential participants will respond to online ads on various social media platforms (Facebook, Instagram, etc.) if they are current e-cigarette users who are interested in quitting and willing to participate in a research study. Clicking on the ad will lead them to a webpage that provides details about what participation in the study entails and describes incentives for participation. Those who are interested will complete an eligibility screener followed by informed consent and a baseline assessment. Those who complete the baseline will be randomized into one of three arms (see below for additional details) and instructed to text a specific keyword corresponding to their treatment assignment to the same phone number. Only those who respond to the first message from the text message program within 24 hours will be fully enrolled into the study. This requirement will be made explicit.

Randomization

Randomization occurs after completion of the online enrollment process (completed baseline survey). A computer algorithm that is part of the survey software will automate random allocation.

Interventions

This is Quitting: Participants will be enrolled to receive messages from This is Quitting as described above.

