Outcome Measures. The primary outcome is self-reported 30-day point-prevalence abstinence (ppa) at 7-months but we will gather abstinence data at all follow-ups. Other quitting-related outcomes include change in motivation to quit, quit attempts, reduction in e-cigarette use, 7-day ppa, and continuous abstinence measured at each follow-up. Intervention satisfaction in both conditions will be measured with items about overall satisfaction and whether they would recommend it to a friend (scale from 0-10). Satisfaction with frequency of text messages will be measured.²⁸ To assess perceived message relevance, participants will be asked whether text messages "were written personally for you"²⁹ and "were directed at you personally".³⁰

Data Analysis Plan

[figure not shown]
Primary Analysis. Point-prevalence abstinence (ppa) at 7-months post-randomization will be compared across the treatment and control groups using logistic regression. All estimates will be adjusted for baseline confounders of the intervention-outcome relationship. We will identify potential moderators (e.g., age, gender, baseline motivation to quit) by analyzing interactions between treatment and selected variables. For

all moderators found to be associated with the primary outcome, we will examine the effects of treatment/moderator interaction terms on outcomes after entering main effects.

Secondary Analyses. Additional outcomes related to abstinence and treatment engagement will also be analyzed with logistic regression as secondary analyses. These include likelihood of making a quit attempt, likelihood of reducing e-cigarette use, and changes in confidence and self-efficacy in quitting e-cigarettes.

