Missing Data. Missing data will be handled in two ways. First, we will conduct an intent-to-treat (ITT) analysis in which participants who have been lost to follow up are assumed to be treatment failures (i.e., vaping). This analysis will be conducted because ITT analyses are common in the smoking cessation literature, despite simulations demonstrating that the approach is neither conservative nor anti-conservative but rather biased in favor of whichever condition contains less missingness. Second, we will supplement the ITT analyses with an analysis that uses a multiple imputation (MI) procedure to minimize bias in estimates and standard errors, under the assumption that outcomes are not missing at random (NMAR) but rather more likely to be missing for treatment failures (i.e., vaping) than treatment successes (i.e. abstinence). Since the magnitude of actual response bias is unknown, we will conduct a sensitivity analysis to evaluate the treatment effect on outcomes under a range of magnitudes, from equal odds of missing (OR=1) to five times more likely to be missing (OR=5).

Mediator Analysis. Our conceptual model is that treatment increases the odds of abstinence by increasing perceived social support and perceived self-efficacy for quitting. Those two constructs will be measured at baseline, 1-month and 7-months post-treatment. Change in those constructs from baseline will be evaluated with separate mediation analyses as presented in Figure 1. Specifically, we hypothesize that the effect of treatment on abstinence will be mediated by perceived social support and perceived self-efficacy, such that: (1) a significant effect A is found associating X with Z; (2) a significant effect B is found associating Z with Y; (3) a significant effect C is found associating X with Y; and (4) the effect of C is significantly attenuated when A and B are simultaneously included in the model.

PROTECTION OF HUMAN SUBJECTS

Human Subjects Involvement, Characteristics, and Design

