Communication with DSMB members will be primarily through the principal investigator (PI, [name]) and the research director ([name], MSPH). We will use project management software (Basecamp) and cloud-based file storage (Dropbox) to facilitate communications, track feedback, circulate meeting agendas, and document meeting minutes. The DSMB will have a Chair who will lead the discussion at each meeting. Truth Initiative staff will prepare summary of DSMB meeting minutes for review by full DSMB board following each meeting.

At the first meeting, review of the study protocol will include review of the statistical analysis plan. The DSMB should discuss the adequacy of that plan. The final plan, whether part of a research protocol or separate document, will be maintained as an appendix to this charter. The DSMB should discuss the statistical monitoring procedures they propose to follow to guide their recommendations about termination or continuation of the trial. These procedures could include guidelines for early termination for benefit, termination for futility, and termination for safety reasons.

Regulatory and Ethical Considerations

This study targets health topic that is currently receiving significant media and regulatory attention (ecigarette use). We do not anticipate any regulatory changes that may occur during the study period to impact study conduct as our study is aimed at evaluating a cessation program for a product that may become less

available and fits well into the currently developing regulatory environment.

The assessment-only arm was selected as the most ethical control group for the current study that allows for evaluation of the intervention while keeping control arm participants engaged. We are also adding a Waitlist control to evaluate the impact of regular assessment on outcome. Both control groups will have access to the program at the conclusion of the study if they are interested.

Our payment structure was developed to incentivize participants for their time and increase retention while not creating any coercion. Thus, the incentives are nominal amounts, but provides choices for participants that we hypothesize will lead to great retention.

The current study is a low risk, sociobehavioral only intervention and we do not anticipate any other ethical considerations.

REFERENCES

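### Does the waitlist arm need a written contrast, and a rule for reading it if follow-up differs by arm?

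*Combined protocol and SAP*

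**What the plan says.** The study aims, at the end of the background, describe a two-arm randomized trial of This is Quitting against an assessment-only control. They then add a third group: "We will also include a waitlist control arm to evaluate the influence of assessment reactivity and retention incentives". They say of it, "This arm was not included in sample size calculations". The Subjects section randomizes 1800 participants "to the two main intervention arms (900/arm") and aims for 450 on the waitlist. Regulatory and Ethical Considerations gives the purpose more narrowly: "We are also adding a Waitlist control to evaluate the impact of regular assessment on outcome".

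Under Interventions and Payment for participation, the waitlist arm is contacted only at months 1 and 7. The paid interim texts go to the other two arms. Potential Problems and Solutions expects at least 65% follow-up at month 7 in those two arms and gives no figure for the waitlist.

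Primary Analysis says abstinence "will be compared across the treatment and control groups using logistic regression". Neither it nor Secondary Analyses names the waitlist. The Missing Data section opens "Missing data will be handled in two ways". In the first analysis, "participants who have been lost to follow up are assumed to be treatment failures (i.e., vaping"). The second, described as a supplement, is multiple imputation with the odds of being missing for vapers relative to abstainers ranging from 1 to 5. The section concedes that the first method favors the arm with less missing data.

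**The concern.** An arm of 450 minors has a stated question and no stated analysis. No contrast, outcome or exploratory label is written for it, so these would be settled after the data are in. The word control is also loose: Primary Analysis does not say which control, and the ethics section, in "Both control groups will have access to the program at the conclusion of the study if they are interested", uses one phrase for assessment-only and waitlist together.

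The contrast is also exposed to differential response. The waitlist differs from assessment-only in having no monthly texts and no payments for them. Those are the features under study, and they may also affect who answers at month 7. The maximum payment is 2 × ($20 + $10) + 7 × $5 = $95 in the other two arms and 2 × ($20 + $10) = $60 on the waitlist. If follow-up differs, counting non-responders as vaping mixes a response difference with any real reactivity. Imputation with the wrong odds ratio can err in the opposite direction. A reader could take an artifact for reactivity, or miss reactivity that is there.

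**Working it through.** **1. Is the main comparison in doubt?** The aims call the study two-arm and name the assessment-only control. Subjects speaks of two main arms of 900. The aims leave the waitlist out of the sample size. Measures speaks of both arms, and Outcome Measures of both conditions. Against this stand one unspecific phrase in Primary Analysis and one sentence about later access to the program. Pooling the two controls is not a natural reading.

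**2. How large could the response artifact be?** The plan has no figure to reproduce here, so these are illustrations.

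Inputs:
- Assessment-only follow-up f = 65% (Potential Problems and Solutions, stated as a minimum).
- Assessment-only abstinence with missing counted as vaping = 18.6%. This is the control rate in the earlier trial at ages 18–24; the protocol does not say which abstinence definition or time point it refers to.
- 900 versus 450 participants (Subjects).
- Assumptions: waitlist follow-up of 55% to 75%, the same true abstinence p in both arms, and the same odds ratio k of being missing for vapers versus abstainers.

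Abstinence among responders is r = 18.6/65 = 28.6%. True abstinence is p = r·f + (1 − f)/(1 + k(1 − r)/r). For k = 2: 0.186 + 0.35/(1 + 2 × 0.714/0.286) = 0.186 + 0.058 = 24.4%. For k = 1 and k = 5, p is 28.6% and 21.2%.

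Hold p and k fixed. For each waitlist follow-up F, solve p/(1 + o) + (1 − p)/(1 + k·o) = F for the abstainers' odds of being missing, o. Waitlist abstinence under missing-equals-vaping is then p/(1 + o). Example with k = 1 and F = 55%: 0.286 × 0.55 = 15.7%, so the difference is 18.6 − 15.7 = +2.9 points.

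| Waitlist follow-up | k = 1 | k = 2 | k = 5 |
|---|---|---|---|
| 55% | +2.9 | +2.1 | +1.2 |
| 60% | +1.4 | +1.0 | +0.6 |
| 65% | 0 | 0 | 0 |
| 70% | −1.4 | −1.0 | −0.5 |
| 75% | −2.9 | −1.9 | −1.0 |

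Entries are assessment-only minus waitlist, in percentage points, with no true effect.

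**3. What does the planned imputation do?** With the correct k it returns 0. With a wrong common k inside the planned range it leaves −3.0 to +2.1 points at 55% waitlist follow-up, and −2.1 to +2.5 at 75%. Opposite signs can occur: if the true k is 5, F is 55% and k = 1 is assumed, missing-equals-vaping gives +1.2 and imputation −3.0. The planned range also includes k = 5, where imputation gives 0.

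**4. Against the precision of the contrast.** At equal follow-up the 95% half-width under missing-equals-vaping is 1.96 × √[0.186 × 0.814 × (1/900 + 1/450)] = 4.4 points. For imputation at k = 1, using 585 and 292.5 responders, it is 1.96 × √[0.286 × 0.714 × (1/585 + 1/292.5)] = 6.3 points. At a 10-point follow-up difference, every shift above is smaller than its half-width.

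**5. Would a fixed reading rule help?** The obvious rule trusts the direction when both methods agree on it. Suppose there is no effect, true abstinence is 24.4% and follow-up 65% in both arms, but k is 2 in one arm and 1 in the other. Missing-equals-vaping is then off by 2.7 points and common-k imputation by 3.2 to 4.2, in the same direction. In 20,000 simulated trials of 900 versus 450, the two methods agreed in direction across the whole range of k in about 95% of runs. Agreement is therefore no evidence of reactivity, and fixing this rule in advance would gain nothing.

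**The case for a change.** The strongest opposing case is that the arm exists for one question, that its answer is sensitive to response differences, and that a few sentences written now would cost almost nothing and remove a choice made after the fact. Being unpowered argues for an exploratory label, not for silence.

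Much of this stands. These documents name no waitlist contrast, and the contrast cannot separate the monthly texts from their payments. Differential follow-up is plausible. It is not established, because survey payments, reminders, phone calls and social-media contact carry no stated arm limit.

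The freedom left to the analyst is narrower than it looks. The primary outcome is fixed as 30-day abstinence at month 7. The missing-data methods are ordered, with imputation as the supplement, and the range of odds ratios is set. The Data and Safety Monitoring Board section also allows the final analysis plan to be a separate document, so the most that can be said is that no waitlist analysis appears here.

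**Conclusion.** No change follows. This is missing detail for an auxiliary arm, and no stated rule gives a wrong result. The main effect, This is Quitting versus assessment-only, does not use the waitlist arm and is unaffected. An analyst working from these documents would estimate assessment-only versus waitlist on month-7 30-day abstinence with a 95% interval and label it exploratory. The analyst would report follow-up by arm and apply the two missing-data methods in their stated order. A difference would not be credited to reactivity alone where response may differ by arm.

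Under the assumptions shown, a 10-point follow-up difference moves the waitlist contrast by 1.0 to 2.9 points under missing-equals-vaping, against a half-width of about 4.4. Those figures rest on a control rate from young adults, a follow-up rate stated as a minimum, the target split of 900 to 450, and waitlist follow-up rates that the documents do not give.

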Baseline Variables. To characterize the sample and explore potential moderators of treatment effectiveness, we will gather: additional demographics (student status, employment status); current ecigarette use and history (frequency and rate, 16,17 age of first use, motivation to quit and quitting history 18); nicotine dependence will be assessed with the Penn State Electronic Cigarette Dependence Index 19, EDS/PROMISE-E, 20 the Hooked on Nicotine Checklist, 21 and the E-cigarette Fagerström Test of Cigarette Dependence (e-FTCD) 22; other substance use (other tobacco products, alcohol) and mental health symptoms 23; and adverse childhood events. 24,25 For co-morbidities and adverse childhood events, we chose measures that are validated for use among adolescents. In order to minimize risk to participants, we deliberately avoided measures or deleted questions that assessed sensitive topics such as suicidality. Given evolving trends of e-cigarette use and perception, we will also ask about perception about harm from e-cigarettes, reasons for wanting to quit, and reasons for joining the study. To account for potential predictors of dropout, we will ask about motivation to use or quit e-cigarettes and potential barriers to quitting (e.g., social influences). We will assess baseline levels of perceived level of social support, 26,27 perceived social norms, and perceived self-efficacy for quitting and examine changes in these variables as potential mediators of treatment effectiveness.

Mediating Variables. We hypothesize that treatment engagement will mediate the relationship between treatment assignment and abstinence outcomes. We will extract data regarding replies to interactive text messages (e.g., setting a quit date, keyword use) as well as unsubscribe status, number of days enrolled, and total number of messages received. All text message interactions are date/time stamped.

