The DSMB is responsible for safeguarding the interests of study participants, assessing the safety and efficacy of study procedures, and for monitoring the overall conduct of the study. The DSMB is an independent advisory group to Truth Initiative, and is expected to provide recommendations about starting, continuing, and stopping the study. In addition, the DSMB is asked to make recommendations, as appropriate, to Truth Initiative about:

- Selection, recruitment, and retention of participants
- Completeness, quality, and analysis of measurements
- Participant safety
- Adherence to protocol requirements
- Efficacy of the study intervention
- Benefit/risk ratio of procedures and participant burden, and
- Amendments to the study protocol and consent forms

DSMB meetings will be held via remote connections. The purpose of the first meeting is to review and discuss the DSMB Charter, to provide an overview of study activities, to review and make recommendations about the protocol, and to determine the frequency of interim analyses and whether data will or will not be masked to identity of randomized groups. Enrollment in the study will not begin until the DSMB's Charter has been accepted by the DSMB members, and IRB approval has been obtained.

Meetings will be held approximately once a month prior to study launch, with additional meetings or conference calls scheduled as needed. Before each meeting, when the agenda is sent out, Truth Initiative staff will ask all DSMB members to state whether they have developed any new conflicts of interest since the last meeting. If a new conflict is reported, the Chair and other members will determine if the conflict limits the ability of the DSMB member to participate in the discussion. The DSMB also will review adverse event data, other safety data, enrollment data, and quality and completeness of study data at each meeting to ensure proper trial conduct. At intervals, as noted above, the DSMB will also review formal interim analyses of the primary end point. It is expected that all DSMB members will attend every meeting and call. However, it is recognized that this may not always be possible. Quorum for voting is considered to be half the number of standing members plus one. The Board may wish to decide if particular expertise is needed within the quorum for the meeting to be valid. All standing Monitoring Board members are voting members. A quorum of this DSMB is considered to be: Three (3).

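### The primary model adjusts for baseline confounders, which is the wrong basis after random allocation; a fixed prognostic set would use power that this wording probably leaves unused

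*Combined protocol and SAP*

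**What the plan says.** The Primary Analysis paragraph of the Data Analysis Plan compares 7-month abstinence between arms by logistic regression and adds: "All estimates will be adjusted for baseline confounders of the intervention-outcome relationship". The visible text names no covariate, selection rule or threshold.

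On allocation, the Randomization section says: "A computer algorithm that is part of the survey software will automate random allocation". It follows the baseline survey: "Those who complete the baseline will be randomized into one of three arms".

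Candidate covariates are plentiful. Under Baseline Variables, for example, "nicotine dependence will be assessed with the Penn State Electronic Cigarette Dependence Index" and with three further instruments. These variables are described as characterising the sample or as possible moderators, dropout predictors or mediators. None is assigned to the primary model.

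Two other places bear on the point. Recruitment and Enrollment counts a person as fully enrolled only after a reply to the first text message within 24 hours, and that step comes after assignment and uses an arm-specific keyword. The DSMB section allows for a statistical plan held elsewhere: "The final plan, whether part of a research protocol or separate document, will be maintained as an appendix to this charter".

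**The concern.** A confounder is a cause of the outcome that is also associated with treatment assignment for some reason other than chance. After automated randomisation no baseline variable has that property among those randomised. Applied literally, the sentence selects nothing. Applied as analysts usually apply such wording, it selects variables that happen to be imbalanced.

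The sound reason to adjust in a randomised trial is that a variable predicts the outcome, whether or not it is balanced. An imbalance rule ignores prognostic strength, so it usually omits the variables that would help. It also needs a cut-off, and two analysts with different cut-offs can reach different verdicts on the same data. At stake are a few points of power on the primary comparison and a primary analysis that cannot be reproduced from the visible text.

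**Working it through.** **Inputs from the documents.** 900 per main arm (Subjects). Missing outcomes are counted as vaping (Missing Data), so all 900 per arm enter the analysis. From the earlier young adult trial: "abstinence rates were 24.1% among participants assigned to the intervention (This is Quitting) and 18.6% among participants in the assessment only control arm", OR 1.39 (95% CI 1.15 to 1.68), N = 2,588.

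**Assumptions.** The visible text gives no alpha, target power, planning rates or covariate strengths. I assume two-sided 0.05, carry over the young adult rates, and vary covariate strength.

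**1. Documents' own figures.** OR = (0.241/0.759)/(0.186/0.814) = 1.39. With equal arms of 1,294 (assumed), the Wald interval is 1.15 to 1.68, so the earlier trial's result reproduces. The 900 per arm cannot be reproduced, because its inputs are not given. At the assumed rates, 80% power needs 871 per arm. At 900 per arm:
- null SE = √(2 × 0.2135 × 0.7865/900) = 0.01932
- alternative SE = √((0.241 × 0.759 + 0.186 × 0.814)/900) = 0.01927
- power = Φ((0.055 − 1.96 × 0.01932)/0.01927) = Φ(0.89) = 81.3%

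**2. How often an imbalance rule acts.** With four independent candidates and a p<0.05 cut-off, the chance that none is selected is 0.95⁴ = 81.5%. With p<0.20 it is 0.80⁴ = 41%. At the stricter cut-off, most trials would be analysed unadjusted.

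**3. Simulated power (%).** Logistic regression, Wald test, independent standard normal covariates, marginal rates held at 24.1% and 18.6%. Set-up A has four candidates (20,000 trials per scenario). Set-up B has ten candidates, of which three or five are prognostic (6,000 trials). Set-up C repeats A's covariates with 4,000 trials.

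| Set-up; OR per SD | Unadjusted | Imbalance p<0.05 | Fixed set |
|---|---|---|---|
| A; four at 1.35 | 81.4 | 81.8 | 83.5 |
| A; four at 1.65 | 81.7 | 82.3 | 87.0 |
| A; none prognostic | 81.5 | 81.5 | 81.4 |
| B; three at 1.2 | 82.2 | – | 82.6 |
| B; three at 1.3 | 80.8 | – | 81.9 |
| B; three at 1.5 | 82.0 | – | 84.9 |
| B; five at 1.5 | 81.3 | – | 86.0 |
| B; three at 2.0 | 81.7 | – | 88.8 |
| C; four at 1.35 | – | 79.3 | 80.9 |
| C; four at 1.65 | – | 80.3 | 85.9 |

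Monte Carlo error is about 0.3 point in A, 0.5 in B and 0.6 in C. For OR 1.3 to 1.65 per SD the gains run from 81.9 − 80.8 = 1.1 to 85.9 − 80.3 = 5.6 points.

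**4. Where the gain comes from.** In set-up A the mean unadjusted log-OR over its SE is ln(1.390)/0.1160 = 2.84. With the fixed set it is ln(1.419)/0.1197 = 2.92 or ln(1.468)/0.1254 = 3.06. The SE rises slightly, but the conditional log-OR rises more. The gain is in power, not in a narrower interval.

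**5. Type I error (18.6% in both arms).** Set-up A, at OR 1.35 and 1.65: unadjusted 5.0% and 5.3%; imbalance p<0.05 4.8% and 5.0%; imbalance p<0.20 4.7% and 4.6%; fixed set 5.0% and 5.2%. Set-up B's fixed set gave 4.9% to 5.3%.

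**6. Dependence on the cut-off.** With a true effect, the significance verdict under the p<0.05 imbalance rule differs from the fixed set in 4.7% (OR 1.35) and 7.3% (OR 1.65) of trials. It differs between the p<0.05 and p<0.20 rules in 2.5% and 3.7%.

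**7. A different comparator.** Under a 10% change-in-estimate rule (set-up B, 1,500 trials, error about 1 point), power for the fixed set against that rule was 82.5 vs 82.5, 82.9 vs 83.2, 85.9 vs 85.5 and 88.2 vs 88.1. There is no gain.

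**The case against.** **The imbalance rule is a reading, not the text.** The plan states no rule. The sentence could mean a change-in-estimate rule, against which the fixed set gains nothing, or be loose wording for prognostic variables. This stands, and it limits the size of the claim. It does not rescue the wording, because an analyst still cannot tell which of these is meant.

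**Chance imbalance is not the whole story.** A reader might infer that arms can differ only by chance in whatever set is analysed. The documents do not support that. The 24-hour reply comes after assignment, and the human subjects section describes the 1,800 as people who complete enrolment in the text program, whereas Measures refers to all randomised participants. If only repliers are analysed, systematic differences are possible. Covariate adjustment would not fully repair them, so this argues for stating the analysis set as well.

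**The power range rests on assumptions.** This stands too. The rates come from 18- to 24-year-olds. Four covariates at OR 1.65 imply a baseline-only AUC of about 0.75, which is demanding. If only two of the four are prognostic at OR 1.35, the gain over no adjustment is about 0.8 point.

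**A list may exist.** The DSMB section allows for a separate final plan. If it names covariates, the remedy is a citation.

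**Conclusion.** The stated basis for adjustment is wrong for a randomised comparison, and a fixed prognostic set is better at almost no cost. Under the assumed rates, with three to five covariates at OR 1.3 to 1.65 per SD, it adds about 1 to 6 points of power over no adjustment or a p<0.05 imbalance rule. The gain is near 0 for weak covariates or against a change-in-estimate rule, and about 7 points at OR 2.0. If no covariate is prognostic, nothing measurable is lost. The sentence should be changed, but the benefit is modest and confidence in its size is moderate.

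Two stronger readings are tempting and are not supported:
- A reader might infer that the present wording inflates type I error. Mechanical imbalance rules do not. Inflation needs covariates chosen by their effect on the treatment result, which the text does not describe.
- A reader might infer from "all moderators found to be associated with the primary outcome, we will examine the effects of treatment/moderator interaction terms" that moderators are screened on association with abstinence before interactions are tested. The preceding sentence says moderators are identified through the interactions themselves, so no such screen is clearly stated.

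**What to change.** Replace the sentence with a short fixed set of prognostic baseline variables already collected. Vaping frequency, one named dependence score, motivation to quit and age would be an example; the investigators should choose. State that:
- the set applies regardless of observed balance and is fixed before outcomes are seen by arm;
- the analysis includes all randomised participants, whether or not they replied within 24 hours;
- skipped baseline items are handled by a named method (these should be few, since baseline completion precedes randomisation);
- the unadjusted estimate is reported beside the adjusted one, with a note that the adjusted OR is conditional and differs slightly (in the simulations 1.42 or 1.47 against 1.39).

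If a separate final plan lists covariates, cite it instead.

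The cost is a wording change, with no new data. Timing matters: "At intervals, as noted above, the DSMB will also review formal interim analyses of the primary end point". Board members must be independent of the study, so such a review does not by itself show that the analysts have seen results by arm. If they have, keep the unadjusted comparison primary and label the adjusted one supportive.
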